3.4 Outcomes

This trial will have two primary outcomes, one around essential components for ANC, and one for essential components for PNC.

Outcome 1 (ANC): Essential components included in the composite measure of integrated services specific to ANC visits are listed below.

- EC1 = Respectful maternity care indicators:
 - Introductions, greeting the woman, consent, questions
- EC2 = Screening for Pre-eclampsia:
 - Measure BP

- Test urine for proteinuria
- EC3 = Screening for, prevention and management of Anaemia:
 - Measure Haemoglobin
 - Provide ferrous sulphate with folic acid
- EC4 = Screening for, prevention and management of Malaria:
 - Checked for clinical symptoms and test for Malaria if relevant
 - Provide treatment if needed
 - Provide bed nets if not provided yet
 - Provide Intermittent Presumptive treatment
- EC5 = Screening for, prevention and management of HIV:
 - Test for HIV
 - Provide Prevention of mother to child transmission care (PMTCT)
 - Provide anti-retroviral drugs (ARV) for mother if needed
- EC6 = Screening for, prevention and management of Syphilis:
 - Test for syphilis
 - Provide antibiotics if needed
- EC7 = Screening for, prevention and management of Tuberculosis (TB):
 - Checked for clinical symptoms and test for TB
 - First line TB drugs or referral if needed
- EC8 = Prevention of Tetanus in mother:
 - Tetanus toxoid vaccination
- EC9 = Screening and counselling for mental health and domestic violence:
 - Screening tools
 - Counselling services
- EC10 = Estimation of BMI:
 - Assess maternal height
 - Assess maternal weight
- EC11 = Prevention of post- and pre-term birth:
 - Estimate gestational age
- EC12 = Assessment of foetal wellbeing during pregnancy, Screening for multiple pregnancy, abnormal lie and presentation during pregnancy:
 - Assess growth using fundal height measurement
 - Assess foetal heart rate (FHR)
 - Abdominal palpation
- EC13 = Provide advice on birth preparedness and danger signs of pregnancy:
 - Consultation

The outcome for each ANC visit will be a score which measures the proportion of the above components that was delivered during that visit (EC_ANC).

The score will measure the proportion of essential components delivered in full. All thirteen essential components listed above are applicable for ANC. Some essential components

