involve multiple components, at least one of which is always applicable; some components are only applicable to a subset of clients, eg HCP counsels the woman about mental health is only applicable if the client's response to a previous question is cause for concern. All essential components will carry a weight of 1. The overall score will be derived by aggregating the weighted scores for each essential component which will then be converted to a percentage. Six essential components are binary; hence the score can only be 0 (not achieved), or 1 (achieved and single weighted); in some cases the determination of this involves an algorithm. The other seven essential components are not binary as they have sub-components assessed independently and thus may be partially achieved and carry an intermediate score, eg a multiple of 0.25 for essential component 1 (respectful maternal care).

Outcome 2: Essential components included in the composite measure of integrated services specific to PNC visits are listed below.

- EC1b = Respectful maternity care indicators:
 - Introductions, greeting the woman, consent, questions
- EC2b = Screening for Pre-eclampsia:
 - Measure BP
- EC3b = Screening for, prevention and management of Anaemia:
 - Measure Haemoglobin
 - Provide ferrous sulphate with folic acid
- EC4b = Screening for, prevention and management of Malaria:
 - Checked for clinical symptoms and test for Malaria if relevant
 - Provide bed nets if not provided yet
- EC5b = Screening for, prevention and management of HIV:
 - Test for HIV
 - Provide Prevention of mother to child transmission care (PMTCT)
 - Provide anti-retroviral drugs (ARV) for mother and baby
- EC6b = Screening for, prevention and management of Syphilis:
 - Test for syphilis
 - Provide antibiotics if needed
- EC7b = Screening for, prevention and management of Tuberculosis (TB):
 - Checked for clinical symptoms and test for TB
 - First line TB drugs or referral if needed
- EC8b = Prevention of Tetanus in mother and baby:
 - Tetanus toxoid vaccination
- EC9b = Screening and counselling for mental health and domestic violence:
 - Screening tools
 - Counselling services
- EC10b = Provide advice and support regarding breastfeeding:
 - Consultation

- EC11b = Offer postpartum contraception:
 - Consultation
- EC12b = Monitor newborn growth:
 - Weigh the baby
- EC13b = Clinical examination of the mother:
 - Examine the mother
- EC14b = Clinical examination of the baby:
 - Examine the baby

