Appendix 2: Tools for data collection for observation

Below is the observation checklist. Essential components are numbered slightly differently than appendix 1 for the construction of the score. The scoring attributes will not appear for the data collectors and only be used by the statistician at time of analysis. Each essential component is score 1, for a total of 13 essential components for ANC visits, and 16 for PNC visits. Essential components can be a sum of x number of subcomponents as indicated in the table. Each subcomponent needs all applicable questions to be observed (Please see examples of algorithms at the end of appendix).

Please note this tool is to be deployed on an electronic platform, therefore the formatting of the tool will be visually different to what is included here. All boxes starting with "If" will only appear depending on the answer to the relevant condition (e.g. treatment will only be asked for women tested positive). The "Not applicable" answer is available for questions which depend on the gestational age and type of visit. The tool will be deployed in FRENCH.

OBSERVATION

Variable label	Answers	Conditionality	Scoring
GENERAL			
Please select the region	[dropdown menu]		
Please select the name of the facility	[dropdown menu]		
If 'Other' facility, please specify	[free text]		
Date of survey	[select from calendar]		
Name of person completing form	[free text]		
Anonymous ID of HCP	[free text]		
ANC			
ANC general information			
First/subsequent contact	0 - Subsequent contact, 1 - first contact -99 INF		
Which subsequent visit was it?	2- ANC2, 3- ANC3, 4- ANC4, 5- ANC5, 6-ANC6, 7- ANC7, 7-ANC8	Only to appear if previous answer = 0 – Subsequent visit	
Gestational age (weeks)	[integer]		
Who gave information about gestational age	1 - Woman, 2 - Healthcare provider, 3 - Other (specify)		
If other, specify	[free text]		
Women arrival time in the facility	[time]		
Comments	[free text]		

ANC contact		
EC1: Respectful maternity		1 (sum of all
care		subcomponents)
RMC subcomponent 1		0.25 (Points given if all applicable questions are observed)
The healthcare provider		
(HCP) introduced		
themselves to the		
pregnant woman	0 - No, 1 - Yes	
The HCP greeted the		
pregnant woman (or		
answered if woman		
greeted first)	0 - No, 1 – Yes	
RMC subcomponent 2		 0.25
The HCP asked the		
pregnant woman to take a	0 - No, 1 - Yes, -88 - Not	
seat	applicable (no chairs)	
The HCP asked the		
pregnant woman if she		
came with a companion		

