(or the woman already		
declared it herself)	0 - No, 1 – Yes	
If the woman had a		
companion with her, was		
the companion allowed to		
be with the pregnant		
woman during ANC	0 - No, 1 - Yes, -88 - Not	
consultation?	applicable (no companion)	
RMC subcomponent 3		0.25
The HCP asked how the		
pregnant woman was and		
asked about any problems	0 - No, 1 - Yes,	
RMC subcomponent 4		0.25
The HCP explained to the		
woman what they would		
like to do, prior to all		
examination or		
investigation	0 - No, 1 - Yes,	
The HCP explained that the		
findings of any		
examination and/or		
investigation would be	0 - No, 1 - Yes, -88 - Not	
confidential	applicable (no testing)	
The HCP explained the		
findings of investigations		
or examinations to the		
woman	0 - No, 1 – Yes	

EC2 = Screening for,			1
prevention and			
management of Anaemia			
Anaemia subcomponent 1			0.5
Blood taken to test	0 - No, 1 - Yes		
haemoglobin level	•		
If yes, HCP recognised and	0 - No, 1 – Yes, -88 Not		
acted upon abnormal	applicable		
findings			
Anaemia subcomponent 2			0.25
Iron tablets and folic acid	0 - No, 1 - Yes		
were given or prescribed			
for the pregnant woman			
Anaemia subcomponent 3			0.25
HCP counselled the	0 - No, 1 - Yes		
woman about dietary			
sources of iron			
Anaemia: Not in scoring			
If the woman was referred,			
what was the reason?	comment		
EC3 = Screening for Pre-			1
eclampsia			
Preeclampsia			0.5
Subcomponent 1			
The pregnant woman had			
her BP measured and			
noted in booklet	0 - No, 1 - Yes	0.1.	
If BP over 140/90 mmHg,		Only to	
HCP recognised and acted		appear if	
upon abnormal findings		answer to	
	0 - No, 1 – Yes, -88 – Not	previous question = 1-	
	applicable (BP normal)	Yes	
Preeclampsia	applicable (Br Hormal)	163	0.5
Subcomponent 2			0.5
The HCP checked urine for			
protein and noted in			
booklet	0 - No, 1 - Yes		
If yes, HCP recognised and	, , , , , , , , , , , , , , , , , , ,	Only to	
acted upon abnormal		appear if	
findings		answer to	
		previous	
		question = 1-	
	0 - No, 1 - Yes	Yes	
Preeclampsia: Not in			
scoring			
If the woman was referred,			
what was the reason?	comment		

EC4 = Screening for,			1
prevention and			
management of Malaria			
Malaria Subcomponent 1			0.5
HCP gave her the SP		Only to	
		appear if after	
	0 - No, 1 - Yes	1 st trimester	
HCP explained why it was		Only to	
important taking the SP		appear if	
		answer to	
		previous	
		question = 1-	
	0 - No, 1 - Yes	Yes	
HCP asked the woman			
whether she has			

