Insecticide treated bed net	0 - No, 1 - Yes		
If no, HCP provided		Only to	
Insecticide treated bed net		appear if	
		answer to	
		previous	
	O No 1 Voc	question = 1-	
Malaria Cubsampanant 2	0 - No, 1 - Yes	Yes	0.5
Malaria Subcomponent 2			0.5
Temperature taken using			
a thermometer and			
recorded in a booklet	0 - No, 1 - Yes		
Malaria testing was	O No 4 Van		
performed	0 - No, 1 – Yes	Onlinks	
If test done, did the		Only to	
woman test positive to malaria?	O No 1 Vos	appear if test performed	
If test was positive,	0 - No, 1 - Yes	•	
·	O No 1 Vos 99 Not	Only to	
antimalarials given to the woman	0 - No, 1 - Yes, -88 - Not applicable (Test negative)	appear if test performed	
If test was negative and	applicable (Test Hegative)	Only to	
woman had fever,		appear if test	
treatment or	0 - No, 1 – Yes, -88 – Not	performed	
complementary exams	applicable (Test positive,	periorined	
prescribed/given and	or test negative and		
noted in booklet	woman had no fever)		
If the woman was referred,	2		
what was the reason?	Comment		
EC5 = Screening for,			1
prevention and			
management of HIV			
If follow-up visit and			
previously tested for HIV,			
HIV antibody status was			
checked and noted in			
booklet	0 - No, 1 – Yes		

If ANC1 or no status	O No 1 Voc 99 Not	Ì	1
If ANC1 or no status	0 - No, 1 – Yes, -88 – Not		
indicated in booklet, HIV	applicable (Status		
testing was performed	indicated in booklet		
HCD as a self-state	already)	0.1.1.	
HCP counselled the		Only to	
woman prior to HIV test		appear if test	
	0 - No, 1 – Yes	performed	
HIV test result was noted		Only to	
in booklet		appear if test	
	0 - No, 1 – Yes	performed	
Did the woman test		Only to	
positive to HIV?		appear if test	
	0 - No, 1 – Yes	performed	
If test positive, first line		Only to	
ARV treatment was		appear if test	
prescribed or given and	0 - No, 1 – Yes, -88 – Not	performed	
noted in booklet	applicable (Test negative)		
If test positive, HCP		Only to	
counselled woman about		appear if test	
PMTCT	O No 1 Ves 99 Net	performed	
	0 - No, 1 - Yes, -88 – Not		
16.11	applicable (Test negative)		
If the woman was referred,			
what was the reason?	comment		
EC6 = Screening for,			1
prevention and			
management of Syphilis			
If follow-up visit, syphilis			
status was checked	0 - No, 1 - Yes		
If ANC1 or no status	0 - No, 1 - Yes, -88 – Not		
If ANC1 or no status indicated in booklet,	0 - No, 1 - Yes, -88 — Not applicable (Status		

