well being (or listened if			
she raised it)	0 - No, 1 – Yes		
If the woman expressed		Only to	
concern about her		appear if HCP	
psychological well-being,		asked or	
ie depression or anxiety,		woman raised	
the HCP counsels the		it	
woman	0 - No, 1 – Yes		
If the woman expressed		Only to	
concern about her		appear if HCP	
psychological well-being,		asked or	
ie depression or anxiety	0 - No, 1 - Yes, -88 - Not	woman raised	
the HCP refers the woman	Applicable (No concerns	it	
for additional support	expressed)	10	
Mental subcomponent 2	Слргеззеці		0.5
HCP asked the woman if			0.5
she is experiencing	0 No 1 Yes		
domestic abuse	0 - No, 1 – Yes	0.1.	
If the woman expressed		Only to	
concern about domestic		appear if HCP	
abuse, the HCP counsels	0 - No, 1 - Yes, -88 - Not	asked or	
the woman	Applicable (No concerns	woman raised	
	expressed)	it	
If the woman expressed		Only to	
concern about domestic		appear if HCP	
abuse the HCP refers the	0 - No, 1 - Yes, -88 - Not	asked or	
woman for additional	Applicable (No concerns	woman raised	
support	expressed)	it	
EC10 = Estimation of BMI			1
If subsequent visit, HCP		Only to	
checked if BMI previously		appear if	
recorded		subsequent	
	0 - No, 1 - Yes	visit	
BMI measured by HCP and	,	If ANC1: This	
noted		is the first	
		question to	
	If ANC1, answers are only	appear	
	= 0 - No, 1 – Yes	аррсаі	
	- 0 - NO, 1 - 165	If subsequent	
	If subsequent visit answers	visit, this is	
	•	the second	
	are = 0 - No, 1 - Yes		
	, -88 - Not applicable (BMI	question to	
If DMI do 40, LICD	already noted)	appear	
If BMI under 18, HCP	0 No 4 Var 00 No		
recognised and acted upon	0 - No, 1 - Yes-88 - Not		
abnormal findings (e.g.	applicable (BMI normal or		
provided nutrition advice	unchecked)	l	I

I	I	I	I .
and supplementation, or			
referred if signs of gravity)			
If BMI over 30, HCP	0 - No, 1 - Yes-88 - Not		
provided nutrition advice	applicable (BMI normal or		
	unchecked)		
EC11 = Prevention of post-			1
and pre-term birth			
HCP noted the gestational			
age in booklet	0 - No, 1 - Yes		
EC12 = Assessment of			
foetal wellbeing during			
pregnancy; Screening for			
multiple pregnancy,			
abnormal lie and			
presentation The HCD measured		Onlyannas	
The HCP measured		Only appears	
symphysis- fundal height		if age of pregnancy >	
	O No 1 Ves		
If fundal haight magazired	0 - No, 1 - Yes 0 - No, 1 - Yes, -88 - Not	16 weeks	
If fundal height measured,			
HCP recognised and acted	applicable (no abnormal		

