woman had fever,	O No 1 Voc 99 Not	appear if test	
treatment or	0 - No, 1 - Yes, -88 – Not	performed	
complementary exams	applicable (Test positive,		
prescribed/given and noted in booklet	or test negative and woman had no fever)		
SF5b = Screening for,	woman nau no rever)		1
prevention and			1
management of HIV			
HIV antibody status was			
checked	0 - No, 1 - Yes		
If no status indicated in	0 - No, 1 - Yes, -88 – Not		
booklet, HIV testing	applicable (Status		
performed	indicated in booklet		
·	already)		
HCP counselled the		Only to	
woman prior to HIV test		appear if test	
	0 - No, 1 – Yes	performed	
HIV test result was noted		Only to	
in booklet		appear if test	
	0 - No, 1 - Yes	performed	

Did the woman test	I	Only to	1
		•	
positive to HIV?	0. No. 4. Was	appear if test	
15.1	0 - No, 1 - Yes	performed	
If the mother is HIV		Only to	
positive, first line ARV		appear if test	
treatment for mother was		performed	
prescribed or given and	0 - No, 1 - Yes, -88 – Not		
noted in booklet	applicable (Test negative)		
first line ARV treatment for		Only to	
mother was provided		appear if test	
		performed on	
		mother and	
	0 - No, 1 – Yes	positive	
	0 - No, 1 – Yes	Only to	
HCP performed HIV testing		appear if test	
for baby(ies) with nucleic		performed on	
acid testing		mother and	
acia testilig		positive	
If the baby(ies) nucleic		Only to	
1			
acid test is positive ART for	0 No 1 Ves 00 Net	appear if test	
baby commenced,	0 - No, 1 - Yes, -88 – Not	performed on	
	applicable (baby Test	mother and	
	negative)	positive	
If the baby(ies) nucleic acid		Only to	
test is positive the mother		appear if test	
is given PMTCT advice		performed on	
about exclusive	0 - No, 1 - Yes, -88 – Not	mother and	
breastfeeding or	applicable (baby Test	positive	
replacement feeding	negative)		
EC6b = Screening for,			1
prevention and			
management of Syphilis			
Syphilis status was			
checked	0 - No, 1 – Yes		
If no status indicated in	0 - No, 1 - Yes, -88 – Not		
booklet, syphilis testing	applicable (Status		
was performed	indicated in booklet		
was performed	already)		
did the woman test	ancadyj	Only to	
positive for syphilis?		appear if test	
positive for syptims!	O No 1 Vos	performed	
If heat maritime and the con-	0 - No, 1 – Yes	+ '	
If test positive, antibiotic		Only to	
treatment was prescribed		appear if test	
(or prescribed if not		performed	
available in facililty) and			
noted in booklet	0 - No, 1 – Yes		
EC7b = Screening for,			1
prevention and			
management of			

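### The ANC urine row and the ANC and PNC bed-net rows cannot record that follow-up was not needed, so care of women with normal urine or an existing net cannot be scored reliably or repaired later

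*Protocol*

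**What the plan says.** Section 3.4 defines two primary outcomes: an ANC score over 13 components and a PNC score over 16, each component with weight 1. Components may be split into subcomponents, and the introduction to Appendix 2 sets the rule: "Each subcomponent needs all applicable questions to be observed". The same introduction says that boxes beginning with If "will only appear depending on the answer to the relevant condition (e.g. treatment will only be asked for women tested positive"). It offers the not-applicable answer for questions that depend on gestational age and type of visit, and does not mention normal findings.

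Section 3.4 makes some acts conditional. For nets it says "Provide bed nets if not provided yet". It also says that "HCP counsels the woman about mental health is only applicable if" an earlier answer gives cause for concern.

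Five rows of the Appendix 2 form matter here:

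- **ANC urine (EC3, subcomponent 2).** After "The HCP checked urine for" protein comes a row on acting upon abnormal findings. It is shown when urine was checked and accepts only 0 or 1.
- **ANC net (EC4, subcomponent 1).** The row "If no, HCP provided" a treated net is shown when the preceding answer is Yes. The preceding question is whether the provider asked about a net.
- **PNC net (EC4b, subcomponent 1).** The label is the same, the answers are 0 or 1, and no condition is given.
- **ANC mental health (EC9, subcomponent 1).** The row in which "the HCP counsels the" woman is shown whenever the topic was asked about or raised, and accepts only 0 or 1.
- **PNC syphilis (EC6b).** The antibiotic row ("available in facililty) and" noted in the booklet) is shown whenever a test was done, and accepts only 0 or 1.

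**The concern.** These rows are shown because a screening step took place, whatever it found, or with no stated condition at all. The observer must then answer No or Yes about an act that was not called for. Sibling rows in the same form show that a not-applicable code was intended for this situation. ANC blood pressure has -88 for a normal reading, ANC haemoglobin has -88, ANC syphilis treatment has -88 for a negative test, and mental-health referral has -88 when no concern was expressed.

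Because one No forfeits the subcomponent, a provider who tests urine and finds it normal can receive the same zero as one who never tested. The ANC net row shares its 0.5 with giving the malaria prophylaxis and explaining it, so a 0 on the net row removes credit for those acts as well. Training is meant to increase screening. If screening of women with normal findings earns nothing, part of the training effect does not reach the primary score. Appendix 2 hides the scoring from the data collectors, of whom section 3.9.1 mentions two, so they cannot see what a 0 or a 1 costs and may settle on different habits.

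**Working it through.** **1. The plan's own score structure.** Adding the Appendix 2 ANC weights:

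- Multi-part components: EC1 4 × 0.25; EC2 0.5 + 0.25 + 0.25; EC3, EC4, EC9 and EC13 each 2 × 0.5; EC7 0.2 + 0.4 + 0.4. Sum 7.
- Single-score components: EC5, EC6, EC8, EC10, EC11, EC12, weight 1 each. Sum 6.

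The total is 13, with six binary and seven multi-part components, as section 3.4 states.

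**2. Row by row.**

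| Row | Shown when | -88 on this row | Is the fact that decides applicability recorded? |
|---|---|---|---|
| ANC urine, 0.5 | urine checked | no | no: urine result not recorded |
| ANC net, 0.5 | provider asked about a net | no | no: ownership not recorded |
| PNC net, 0.5 | no condition given | no | no: ownership not recorded |
| ANC mental health, 0.5 | topic asked about or raised | no | yes: referral row has -88 for no concern |
| PNC syphilis, 1.0 | test done | no | yes: test result is recorded |

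The last column divides the rows. The first three cannot be repaired from the data collected, because Appendix 3 holds only facility totals. The last two can.

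**3. Score for a woman who needed no follow-up.** Under the all-applicable rule:

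- Urine: checked = 1. If follow-up = 0, the subcomponent scores 0. If follow-up is not applicable, it scores 0.5.
- ANC net: prophylaxis given = 1, explained = 1, asked = 1. If provision = 0, it scores 0. If not applicable, 0.5.
- PNC net: asked = 1. If provision = 0, it scores 0. If not applicable, 0.5.

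**4. Points at stake if 0 is entered.**

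- Irreparable, ANC: (0.5 + 0.5)/13 = 0.077, so the maximum attainable score is 12/13 = 92.3%.
- Irreparable, PNC: 0.5/16 = 0.031.
- All five rows coded 0 and none repaired: ANC 1.5/13 = 0.115; PNC (0.5 + 1.0)/16 = 0.094.

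**5. Illustration for the two ANC rows (assumed inputs, not in the protocol).** Suppose training raises correct care in both subcomponents from 30% to 70%, and every observer enters 0 when no follow-up was needed. Let *u* be the share with abnormal urine and *n* the share without a net.

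- True gain: 1.0 × 0.4/13 = 0.031.
- Counted gain: 0.5 × 0.4 × (*u* + *n*)/13.
- *u* = 10%, *n* = 40%: 0.2 × 0.5/13 = 0.008, loss 0.023.
- *u* = 5%, *n* = 30%: 0.2 × 0.35/13 = 0.005, loss 0.025.
- *u* = 20%, *n* = 50%: 0.2 × 0.7/13 = 0.011, loss 0.020.

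For scale, section 3.6 simulates an effect of 0.1 and gives a detectable difference of 0.23 with three providers per facility. The central loss is 0.023/0.1 = 23% of the first and 0.023/0.23 = 10% of the second.

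**The case against.** The strongest reply is that the introduction to Appendix 2 already hides If rows unless their condition holds, and gives treatment after a positive test as its example. Section 3.4 also says that some scores need an algorithm and that mental-health counselling counts only where there is cause for concern. On that reading the syphilis and mental-health rows never apply to women without the condition, and the statistician can enforce this from the recorded test result and the referral code. This stands for those two rows.

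It does not rescue the other three. The urine row's own condition is that urine was checked, so obeying the introduction still shows it to every woman with normal urine. For nets, the only earlier answer is whether the provider asked, and neither No nor Yes to that says whether the woman has a net. An analysis plan that is not at hand may define applicability, but it cannot restore a fact that was not collected. Leaving the row blank is no clear escape, because section 3.8 omits records with missing outcome values.

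A reader might infer that correct care always scores zero and that the estimated effect is certainly biased toward zero. The documents do not fix this. The zero needs the row-level trigger to prevail over the introduction and the observer to enter 0. An observer could equally enter 1, which keeps the credit but reports an act that nobody performed. Nor is every trigger wrong: the PNC net row lacks one, and the blood-pressure row uses the same trigger as urine and works because it carries -88.

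It is also fair that the form is a layout still to be built electronically and pre-tested (sections 3.7 and 3.9.1). That makes the correction cheap but does not supply the missing rows.

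**Conclusion.** The defect is real and narrow. Three rows (ANC urine, ANC net, PNC net) cannot distinguish follow-up that was omitted from follow-up that was not needed, and the information to tell them apart is not collected. Up to 7.7 points of the ANC score and 3.1 points of the PNC score are irreparably exposed. The figures of 11.5 and 9.4 points apply only if all five rows are coded 0 and the two repairable ones are left unrepaired.

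The loss falls on a 0.5 subcomponent (a whole component only for PNC syphilis), never on the whole visit. If observers enter 0 and training increases screening, the bias is toward no effect, because the added screening earns credit only in women who have the trigger. If observers differ, the result is scoring that depends on the observer. The attenuation of 0.020 to 0.025 rests on assumed shares and an assumed training gain, and shows scale only. The PNC mental-health follow-up rows and the worked scoring example could not be read and are not judged.

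**What to change.** Before the form is deployed:

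1. Add two recorded facts: whether urine protein was abnormal (ANC), and whether the woman already has a treated net (ANC and PNC).
2. Show each of the five follow-up rows only when its trigger is present (abnormal urine, no net, concern expressed, positive test), or add -88 with the reason.
3. State in the scoring rule that -88 means not applicable, so that the row drops out of the all-applicable requirement.
4. Reconcile the introduction to Appendix 2 with the Conditionality column, including its limit of the not-applicable answer to gestational age and type of visit.

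The cost is a small edit to the electronic form and the scoring script, and about two extra taps per visit. No visits or staff are added. The mental-health and syphilis rows could still be repaired at analysis, but the urine and net rows could not.

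### The Appendix 2 tool shows HIV and syphilis management rows only when a test is done at the observed visit, so women already known to be positive can earn full credit with no management recorded

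*Protocol*

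**What the plan says.** Section 3.4 lists three elements for HIV: a test, PMTCT care and antiretrovirals. The last is worded "Provide anti-retroviral drugs (ARV) for mother if needed" for ANC and "Provide anti-retroviral drugs (ARV) for mother and baby" for PNC. Syphilis is a test plus antibiotics where needed. None of these is tied to the timing of the test.

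Appendix 2 turns the components into form rows. Its preamble gives, as an example of conditional display, that "treatment will only be asked for women tested positive", and sets the scoring rule: "Each subcomponent needs all applicable questions to be observed".

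At ANC, the first HIV row concerns a follow-up client "previously tested for HIV" and asks whether her status was checked. The testing row applies at a first visit or when no status is "indicated in booklet, HIV"; otherwise it is coded not applicable. The rows for pre-test counselling, result, antiretrovirals (beginning "If test positive, first line") and PMTCT counselling are all displayed only if a test was performed.

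At PNC, the maternal antiretroviral row opens "If the mother is HIV" positive, but its display condition again requires a test to have been performed. The rows for provision of maternal treatment, infant nucleic acid testing, infant treatment and feeding advice require that the mother was tested and was positive. The feeding-advice row, which carries the PMTCT content, also requires a positive infant test. The syphilis result and antibiotic rows have the same test-performed condition on both forms.

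**The concern.** The outcome definition asks whether management was delivered to women who need it. The tool asks only about women whose test took place in front of the observer. At follow-up ANC and at PNC, a positive woman may already have her status in the booklet, and for her every management row is hidden. The visit is then scored on the status check alone.

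Two women with the same unmet need can therefore get opposite component scores, depending only on when they were tested. A later analysis plan cannot repair this. No scored field records that a booklet status was positive, and none records management of such a woman, so the data will not exist. HIV is one of the programme's three focus diseases, so the gap lies in a component that readers will look at.

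**Working it through.** **1. Is the component all-or-nothing?** Section 3.4 says six ANC components are binary. In Appendix 2 exactly six ANC components have no subcomponents: HIV, syphilis, tetanus, BMI, gestational age and foetal wellbeing. HIV and syphilis are therefore binary, and the rule on applicable questions applies to the whole component.

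**2. Score by case, ANC HIV component.** Hidden and not-applicable rows are dropped; the remaining rows must all be Yes.

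| Case | Rows that count | Score |
|---|---|---|
| Known positive, status checked, no ARV or PMTCT counselling | status check | 1 |
| Same woman, if the ARV and PMTCT rows were displayed | status check, ARV, PMTCT | 0 |
| Known positive, status not checked | status check | 0 |
| Tests positive today, counselled and result noted, no ARV or PMTCT counselling | test, counselling, result noted, ARV, PMTCT | 0 |

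Rows 1 and 4 show the inconsistency. The difference is 1/13 = 0.077 of the ANC visit score. At PNC it is 1/16 = 0.063.

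**3. Number of visits.** Section 3.6 (Box 2) gives 18 facilities, 4 assessed periods, 2 or 3 providers and 4 visits per provider for each outcome: 18 × 4 × 2 × 4 = 576 and 18 × 4 × 3 × 4 = 864. This reproduces the 576 to 864 in section 3.5.3. That section presents the figure as the total number of women, while Box 2 and section 3.7 imply it is per outcome. I take it per outcome, which gives the larger count.

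**4. Visits touched, HIV.** Section 2.1.3 gives adult prevalence of 1.6%. The share of attenders already known positive is not given.
- Upper figure, treating every positive woman as already known: 576 × 0.016 = 9.2 and 864 × 0.016 = 13.8.
- ANC, narrowed with section 2.1.3: 3,248 of 6,936 ANC visits were first visits, so follow-ups are 1 − 3,248/6,936 = 0.53. The share tested at booking is 1,791/3,248 = 0.55. Then 9.2 × 0.53 × 0.55 = 2.7 and 13.8 × 0.53 × 0.55 = 4.0.
- The documents allow no similar narrowing for PNC.
- If the known-positive share is anywhere from 0.5% to 5% (an assumption), the range is 576 × 0.005 = 2.9 to 864 × 0.05 = 43.2 visits.

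**5. Shift in the mean score.** The largest possible shift is the share affected divided by the number of components.
- ANC: 0.016/13 = 0.0012 (0.0004 to 0.0038 over the 0.5% to 5% range).
- PNC: 0.016/16 = 0.0010.
- ANC with the narrowed count: 0.016 × 0.53 × 0.55/13 = 0.0004.

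Section 3.6 gives the detectable difference as 0.81 × √(0.01 + 3 × 0.0225) = 0.225, stated as 0.23. The ANC shift of 0.0012 is 0.0012/0.23, about 0.5% of it (0.2% to 1.7% over the range).

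The documents give no figure from which to size the syphilis gap.

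**The case against.** The preamble sentence does not itself limit treatment questions to a test at the observed visit; a woman who tested positive earlier has also tested positive. That is right, and the fault rests on the row conditions. There the testing row is not applicable when a status is on record, so a test-performed condition cannot be met.

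The HIV scoring algorithm is not shown; the only scoring example is for respectful maternity care. This also stands, but no algorithm can use a result or a treatment that no scored field holds.

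A woman on established or completed treatment may need no action that day, so an unmarked management row need not mean care was omitted. This stands and shapes the fix.

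A reader might infer that the trial will hold no information on PMTCT for known-positive women. Appendix 3 does collect pooled facility counts of HIV-positive women receiving prophylactic treatment at ANC and PNC (ea015 and fa010). They are not at visit level and do not enter the score.

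A reader might also infer that more booking tests after training would bias the estimated effect in a known direction. The documents do not support that: full credit requires the status check to be done, and the amount of omitted care before and after training is unknown.

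Finally, no separate analysis of the HIV component is planned, and section 3.7 describes the tools as still to be developed. The first limits the consequences; the second means the change can still be made.

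**Conclusion.** The outcome definition in section 3.4 and the display conditions in Appendix 2 contradict each other and must be reconciled. As the tool is written, management of women with a recorded positive status is unmeasured, and a status check alone earns full credit for the component. At PNC there are two further inconsistencies: the maternal antiretroviral row's label covers any HIV-positive mother but its display condition does not, and the PMTCT advice row needs a positive infant test that section 3.4 does not mention.

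This is a content-validity fault in the visit score. It is not a power problem, and no directional bias in the training effect can be shown. Its numerical effect is small: about 3 to 4 ANC visits, at most about 9 to 14 visits per outcome, and a mean shift of no more than about 0.001. These figures assume that the 1.6% general-adult prevalence applies to attenders, that 576 to 864 visits are observed per outcome, and, for the ANC figure, that the visit mix and booking-test rate from 60 facilities in twelve regions carry over to the N'Djamena sites. It is still worth correcting, because the missing data cannot be recovered once observation starts.

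**What to change.** Before the form is deployed:
- Add a row recording whether the woman's status is positive by today's test or by the booklet, for HIV and for syphilis, on both the ANC and the PNC form.
- Make the maternal antiretroviral, PMTCT, infant and antibiotic rows depend on that status instead of on a test at the visit.
- Give those rows a code for care already documented or completed, so that established treatment is not scored as an omission.
- Reconcile the display condition of the PNC PMTCT advice row with section 3.4, and the PNC maternal antiretroviral row's condition with its own label.

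This changes what is measured and proposes no clinical rule. The cost is four extra rows (two diseases on two forms), revised skip logic and a short booklet check. Section 3.10 already foresees the observer consulting the booklet for a previous HIV status.
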